7.1.2 LOST TO FOLLOW-UP

A participant will be considered lost to follow-up if he or she fails to return for Day 28 Exit visit and is unable to be contacted by the study site staff.

The following actions must be taken if a participant fails to return to the clinic for a required study visit:

- The site will attempt to contact the participant and reschedule the missed Follow-up / Day 28 visit.
- Before a participant is deemed lost to follow-up, the investigator or designee will make every effort to regain contact with the participant.
- Should the participant continue to be unreachable, he or she will be considered to have withdrawn from the study with a primary reason of lost to follow-up.

8 STUDY ASSESSMENTS AND PROCEDURES

8.1 ELIGIBILITY AND EFFICACY ASSESSMENTS

The following assessments will be administered to each eligible participant

Assessment	Purpose	Time to Administer
Eligibility		
MINI-KID	Confirm diagnosis of ADHD and identify any excluding comorbid diagnoses	20 minutes
WISC V	Determine IQ	60 minutes
Ishihara Colorblindness Test	Determine colorblindness	5 minutes
Efficacy		

Assessment	Purpose	Time to Administer
Vanderbilt ADHD Diagnostic Parent Rating Scale	Assess severity of ADHD symptoms and effect on behavior.	20 minutes
Resting State EEG	Assess MFT activity in a resting state	6 min
PDT-locked EEG	Assess MFT activity during a Perceptual Discrimination Task	1 hour
Test of Variables of Attention (TOVA)	Assess objective attention	22 minutes
AKL-M01 (EVO Monitor)	Assess MFT activity during a AKL-M01 session	20 minutes

8.2 SAFETY AND OTHER ASSESSMENTS

Safety assessments will include the evaluation of adverse device effects (ADEs).

8.3 ADVERSE EVENTS AND SERIOUS ADVERSE EVENTS

8.3.1 DEFINITION OF ADVERSE DEVICE EFFECTS (ADE)

An ADE is an adverse event related to the use of an investigational medical device. This includes any adverse event resulting from insufficiencies or inadequacies in the instructions for use, the deployment, the implantation, the installation, the operation, or any malfunction of the investigational medical device. This also includes any event that is a result of a user error or intentional misuse.

8.3.2 DEFINITION OF UNANTICIPATED ADVERSE DEVICE EFFECTS (UADE)

Per 21 CFR 812.3, an Unanticipated Adverse Device Effect is any serious adverse effect on health or safety or any life-threatening problem or death caused by, or associated with, a device, if that effect, problem, or death was not previously identified in nature, severity, or degree of incidence in the investigational plan or application (including a supplementary plan or application), or any other unanticipated serious problem associated with a device that relates to the rights, safety, or welfare of participants.

Unanticipated Adverse Device Effects will include events meeting BOTH A and B as stated below:

- A. Events meeting ALL of the following criteria:
 - 1) Not included in the list of Anticipated Events (refer to protocol Section 8.3.3)
 - 2) Possibly, probably, or definitely related to the investigational device (per the sponsor)
- B. Serious (meets any of the following criteria):
 - 1) Is life-threatening illness or injury
 - 2) Results in permanent impairment of a body function or a body structure
 - 3) Necessitates medical or surgical intervention to prevent permanent* impairment of a body function or a body structure. (***Permanent*** is defined as irreversible impairment or damage to a body structure or function, excluding trivial impairment or damage)
 - 4) Leads to fetal distress, fetal death or a congenital abnormality or birth defect
 - 5) Leads to death.

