8.3.3 PREVIOUSLY KNOWN ADVERSE DEVICE EFFECTS

The expectedness of an ADE shall be determined according to the Instructions for Use and the expected ADEs listed below. Any ADE that is not identified in nature, severity, or specificity in the current investigational product reference documents is considered unanticipated.

Adverse Device Effects expected for this device are as follows:

- Dizziness
- Nausea
- Headache
- Decreased frustration tolerance
- Emotional reaction

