8.3.4.2 RELATIONSHIP TO STUDY TREATMENT

All ADEs must have their relationship to study treatment assessed by the clinician who examines and evaluates the participant based on temporal relationship and his/her clinical judgment. In a clinical trial, the investigational device must always be suspect. The degree of certainty of causal relationship of an adverse device effect of either study treatment will be rated as follows:

- **Possible:** An event that might be due to the use of the study device. An alternative explanation, e.g., concomitant drug(s), concomitant disease(s), is inconclusive. The relationship in time is reasonable; therefore, the causal relationship cannot be excluded.
- **Probable:** An event that might be due to the use of the study device. An alternative explanation is less likely - e.g., concomitant drug(s), concomitant disease(s). The relationship in time is suggestive.
- **Definitely:** An event that is due to the use of the study device. The event cannot be reasonably explained by an alternative explanation - e.g., concomitant drug(s), concomitant disease(s).

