8.4.2 UNANTICIPATED PROBLEM REPORTING

The investigator will report unanticipated problems (UPs) to the reviewing Institutional Review Board (IRB) and to the Data Coordinating Center (DCC)/lead principal investigator (PI). The UP report will include the following information:

- Protocol identifying information: protocol title and number, PI's name, and the IRB project number;
- A detailed description of the event, incident, experience, or outcome;
- An explanation of the basis for determining that the event, incident, experience, or outcome represents an UP;
- A description of any changes to the protocol or other corrective actions that have been taken or are proposed in response to the UP.

An investigator shall submit to the sponsor and to the reviewing Institutional Review Board (IRB) a report of any unanticipated adverse device effect occurring during an investigation as soon as possible, but in no event later than 10 working days after the investigator first learns of the effect (21 CFR 812.150(a)(1)). A sponsor who conducts an evaluation of an unanticipated adverse device effect under 812.46(b) shall report the results of such evaluation to the Food and Drug Administration (FDA) and to all reviewing IRBs and participating investigators within 10 working days after the sponsor first receives

notice of the effect. Thereafter the sponsor shall submit such additional reports concerning the effect as FDA requests (21 CFR 812.150(b)(1)).

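### Section 8.3.2's stepwise UADE rule conflicts with the protocol's own severity and relatedness provisions, leaving it unclear whether a serious event of a listed type needs the 10-working-day report

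*Combined protocol and SAP*

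**What the plan says.** Section 8.3.2 first gives the regulatory definition of a UADE. A serious effect qualifies "if that effect, problem, or death was not previously identified in nature, severity, or degree of incidence in the investigational plan or application". It then sets out a working rule: "Unanticipated Adverse Device Effects will include events meeting BOTH A and B as stated below". Part A has two criteria, both required. A.1 is "Not included in the list of Anticipated Events (refer to protocol Section 8.3.3". A.2 is "Possibly, probably, or definitely related to the investigational device (per the sponsor". Part B lists the outcomes that make an event serious, including life-threatening illness and death.

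Section 8.3.3 introduces its list with "Adverse Device Effects expected for this device are as follows" and names dizziness, nausea, headache, decreased frustration tolerance and emotional reaction. None carries a grade or a rate. The same section also states: "Any ADE that is not identified in nature, severity, or specificity in the current investigational product reference documents is considered unanticipated".

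Section 8.3.4.3 bases expectedness on nature, severity or frequency and leaves the decision to the sponsor. On causality, Section 8.3.4.2 says "All ADEs must have their relationship to study treatment assessed by the clinician", and Section 8.3.6 requires the investigator to assess it. Section 8.4.1 repeats the regulatory definition when it defines unanticipated problems.

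Under Section 8.4.2 the investigator reports a UADE to the sponsor and the IRB "in no event later than 10 working days after the investigator first learns of the effect". Section 8.3.6 separately requires every device effect, anticipated or not, to be reported within 24 hours.

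**The concern.** The definition at the top of 8.3.2 and the rule beneath it ask different questions. The definition asks whether an effect of this nature, severity or incidence was foreseen. A.1 asks whether the name of the event is on a list. Because the list is ungraded, a mild headache and a life-threatening one look the same to A.1.

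A second mismatch concerns who judges relatedness. A.2 names the sponsor, while two other sections name the clinician or investigator, and the reporting clock runs from the investigator's knowledge.

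At stake is the one report to the IRB and FDA for which the protocol sets a deadline. Site staff with a serious event in a child aged 8 to 12 will tend to use the stepwise rule, because it is the only checklist provided. Applied word for word, it can classify as anticipated an event that the rest of the protocol treats as unanticipated.

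**Working it through.** No arithmetic applies and the plan gives no figure to reproduce. The check takes two test events through each provision.

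**Event 1: a life-threatening event of a type named in 8.3.3, which investigator and sponsor agree is possibly device-related.** The protocol's list identifies no severity for it.

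| Provision | Test applied | Result |
|---|---|---|
| 8.3.2, A.1 read literally | Is the name on the list? | Listed, so A fails: not a UADE by this rule |
| 8.3.2, opening definition | Identified in nature, severity or degree of incidence? | Severity not identified: UADE |
| 8.3.3, sentence above the list | Identified in nature, severity or specificity? | Severity not identified: unanticipated |
| 8.3.4.3 | Consistent with prior risk information in nature, severity or frequency? | Severity not described in the protocol: unexpected |
| 8.4.1 | Same test as the opening definition | Unanticipated problem |

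The event meets part B because it is life-threatening, so A.1 alone decides the outcome under the stepwise rule.

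**Event 2: a serious event not on the list, which the investigator judges possibly related and the sponsor judges unrelated.**

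| Provision | Who decides | Result |
|---|---|---|
| 8.3.2, A.2 read literally | Sponsor | Not related, so A fails: not a UADE by this rule |
| 8.3.4.2 | Examining clinician | Related |
| 8.3.6 | Investigator | Related |

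**What follows for reporting.**

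1. UADE report (8.4.2). The investigator owes it to the sponsor and IRB within 10 working days of learning of the effect. The sponsor's evaluation then goes to FDA, the IRBs and the investigators within 10 working days of the sponsor receiving notice. For both test events, whether this chain starts depends on which provision is followed.
2. Unanticipated-problem report (8.4.2). It goes to the IRB and the coordinating center or lead investigator. No deadline is stated for unanticipated problems other than UADEs.
3. Device-effect report (8.3.6). It is due within 24 hours whichever provision is followed. The section names no IRB recipient, and the method for follow-up reports is an unfilled template placeholder.

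So the same event gets opposite answers on item 1, while items 2 and 3 do not supply a dated report to the IRB.

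**The case against.** A fair reading can reconcile much of this. The rule says that UADEs will include events meeting A and B; it does not say that they are limited to them. A.1 refers the reader to Section 8.3.3, where the severity sentence makes an event of unidentified severity unanticipated. The deadline in 8.4.2 attaches to any UADE, without mention of A and B, and the full regulatory definition stands in both 8.3.2 and 8.4.1. The 24-hour report covers every device effect. Expectedness also rests on the Instructions for Use, which are not part of these documents.

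These points defeat three stronger conclusions that a reader might draw:

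- *All five listed effects are exempt from the UADE report at every severity, so the report is lost.* This needs A and B to be exhaustive and A.1 to be read apart from the rest of 8.3.3. Neither is established.
- *The investigator cannot start the clock.* Section 8.4.2 has the investigator submit the report and counts time from the investigator's own knowledge. A.2 conflicts with that; it does not bar the investigator from reporting.
- *Other serious unanticipated problems are left out because part B omits them.* That limb is already in the opening definition and again in 8.4.1.

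What the objection does not remove is the conflict itself. A.1 points to the list, not to the severity sentence, and requires both A and B to be met. If A and B are not the test, nothing tells the user what else qualifies. The assignment of relatedness in A.2 is not explained anywhere.

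**Conclusion.** The point holds as an internal contradiction in a safety-reporting rule. A.1 conflicts with four provisions (the 8.3.2 definition, the 8.3.3 severity sentence, 8.3.4.3 and 8.4.1), and A.2 conflicts with two (8.3.4.2 and 8.3.6). The consequence is an ambiguous duty to make the 10-working-day report for a serious event of a listed type, or for one on which investigator and sponsor disagree about relatedness. It should be corrected, since literal use of the only stepwise rule would misclassify such an event.

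The practical size is probably small. Section 2.3.3 says that no serious adverse events had been reported across several studies of the device, and no efficacy analysis depends on this rule. The protocol excludes children at risk of suicide. A reader might link that screening to the emotional-reaction entry, but nothing says that a suicidal event would be coded under that name.

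The conclusion for Event 1 assumes that the Instructions for Use and other reference documents do not identify the listed effects at a serious grade. If they do, such an event could count as anticipated under the severity-based provisions too, and the conflict over A.1 would narrow. The conflict over A.2 would remain.

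**What to change.** Reconcile the provisions with two line edits in Section 8.3.2:

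- A.1: *not identified in nature, severity or degree of incidence in Section 8.3.3, the Instructions for Use or the other investigational product reference documents*.
- A.2: replace the sponsor-only attribution with *per the investigator or the sponsor*.

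Optionally, add one sentence saying that A and B do not narrow the 21 CFR 812.3 definition quoted above them. That also settles the question about the limb for other serious problems without rewriting part B.

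The cost is a minor amendment with IRB approval. No new procedure or data collection is needed. The downside is possibly some additional expedited reports; the documents give no basis for a number.

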8.3.3 PREVIOUSLY KNOWN ADVERSE DEVICE EFFECTS

The expectedness of an ADE shall be determined according to the Instructions for Use and the expected ADEs listed below. Any ADE that is not identified in nature, severity, or specificity in the current investigational product reference documents is considered unanticipated.

Adverse Device Effects expected for this device are as follows:

- Dizziness
- Nausea
- Headache
- Decreased frustration tolerance
- Emotional reaction

8.3.4 CLASSIFICATION OF AN ADVERSE EVENT

8.3.4.1 SEVERITY OF EVENT

The following guidelines will be used to describe severity of an ADE:

- **Mild** – Events require minimal or no treatment and do not interfere with the participant's daily activities.
- **Moderate** – Events result in a low level of inconvenience or concern with the therapeutic measures. Moderate events may cause some interference with functioning.
- **Severe** – Events interrupt a participant's usual daily activity and may require systemic drug therapy or other treatment. Severe events are usually potentially life-threatening or incapacitating. Of note, the term "severe" does not necessarily equate to "serious".

8.3.4.2 RELATIONSHIP TO STUDY TREATMENT

All ADEs must have their relationship to study treatment assessed by the clinician who examines and evaluates the participant based on temporal relationship and his/her clinical judgment. In a clinical trial, the investigational device must always be suspect. The degree of certainty of causal relationship of an adverse device effect of either study treatment will be rated as follows:

- **Possible:** An event that might be due to the use of the study device. An alternative explanation, e.g., concomitant drug(s), concomitant disease(s), is inconclusive. The relationship in time is reasonable; therefore, the causal relationship cannot be excluded.
- **Probable:** An event that might be due to the use of the study device. An alternative explanation is less likely - e.g., concomitant drug(s), concomitant disease(s). The relationship in time is suggestive.
- **Definitely:** An event that is due to the use of the study device. The event cannot be reasonably explained by an alternative explanation - e.g., concomitant drug(s), concomitant disease(s).

8.3.4.3 EXPECTEDNESS

Akili Interactive Labs, Inc will be responsible for determining whether an adverse event (AE) is expected or unexpected. An ADE will be considered unexpected if the nature, severity, or frequency of the event is not consistent with the risk information previously described for the study treatment.

8.3.5 TIME PERIOD AND FREQUENCY FOR EVENT ASSESSMENT AND FOLLOW-UP

The occurrence of an ADE may come to the attention of study personnel during study visits and interviews of a study participant presenting for medical care, or upon review by a study monitor.

Information to be collected includes event description, time of onset, clinician's assessment of severity, relationship to study product (assessed only by those with the training and authority to make a diagnosis), and time of resolution/stabilization of the event. All ADEs occurring while on study will be documented appropriately regardless of relationship. All ADEs will be followed to adequate resolution.

Any medical condition that is present at the time that the participant is screened will be considered as baseline and not reported as an ADE. However, if the study participant's condition deteriorates at any time during the study, it will be recorded as an ADE.

Changes in the severity of an ADE will be documented to allow an assessment of the duration of the event at each level of severity to be performed. ADEs characterized as intermittent require documentation of onset and duration of each episode.

The Site Principal Investigator will record all reportable events with start dates occurring from the time of enrollment through the final study visit. At each study visit, the investigator will inquire about the occurrence of ADEs since the last visit. Events will be followed for outcome information until resolution or stabilization.

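### The safety rules conflict: device effects are related by definition, yet must be recorded whatever their cause, on a scale with no grade for an unrelated event.

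*Combined protocol and SAP*

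**What the plan says.** Section 8.2 names ADEs as the content of the safety assessment and names no other safety measure. Section 8.3.1 defines the term: "An ADE is an adverse event related to the use of an investigational medical device".

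Section 8.3.4.2 introduces the causality rating with "The degree of certainty of causal relationship of an adverse device effect of either study treatment will be rated as follows" and then lists three grades: Possible, Probable and Definitely. There is no grade for unlikely or not related. Possible, the lowest grade, requires that any alternative explanation be inconclusive, and it ends: "The relationship in time is reasonable; therefore, the causal relationship cannot be excluded".

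Section 8.3.5 sets the recording rules:

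- On scope: "All ADEs occurring while on study will be documented appropriately regardless of relationship".
- Conditions present at screening count as baseline and are not reported, with this exception: "However, if the study participant's condition deteriorates at any time during the study, it will be recorded as an ADE".
- The investigator records reportable events "with start dates occurring from the time of enrollment through the final study visit".

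Section 8.3.6 places the 24-hour reporting duty on ADEs, anticipated or not.

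Two features of the design bear on this. Section 4.1 describes a single-arm, open-label pilot. Section 5.1 (criterion 6) admits children who stop stimulant medication before baseline and stay off it through the post-training assessment.

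**The concern.** A safety record normally takes in all adverse events first and judges causality second, on a scale that allows the answer no. Here relatedness is built into the unit that is recorded, and the scale leaves out that answer. Two raters who both follow the protocol could treat the same event in opposite ways. One, following 8.3.5, enters it as a device effect. The other, following 8.3.1, decides that it is not device-related and has no instruction to enter it at all.

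The deterioration sentence is more than loose drafting. It is a mandatory rule that assigns events to the device without asking about cause. It matters in this population because some children come off stimulants shortly before baseline, so return of symptoms is a foreseeable non-device reason for worsening.

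What is at stake is whether the study can give a clean account of device-related events or a complete account of all events. The primary EEG endpoint is not affected.

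**Working it through.** The plan states no safety rate, so there is no figure to reproduce. The check follows each kind of event through the definition (8.3.1), the scale (8.3.4.2), the recording rule (8.3.5) and the reporting rule (8.3.6).

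**Case A: an unrelated new event after Day 0.** Under 8.3.1 it is not an ADE, and no rule requires it to be recorded. Under the scope sentence in 8.3.5 it is arguably to be recorded, but then as an ADE. The scale has no grade for it, because even Possible needs an inconclusive alternative explanation.

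**Case B: worsening of a condition present at screening, starting after Day 0, with a clear non-device cause.** Section 8.3.5 makes it an ADE by rule: "condition deteriorates at any time during the study, it will be recorded as an ADE". Under 8.3.1 that label says it is device-related. Under 8.3.4.2 it meets none of the three definitions. It is therefore an ADE with no valid grade.

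**Case C: the same worsening with an uncertain cause.** It is an ADE by rule and can properly be rated Possible. The three sections agree in this case.

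**Case D: worsening that starts during washout, before Day 0.** The Schedule of Activities (1.3) puts the washout screening visit at Day -7 to -3 and enrollment at Day 0. The baseline state is fixed at screening, but recording starts at enrollment. Worsening in between is probably not recorded, although the wording on deterioration at any time in the study can be read to include it. The text does not settle the matter.

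Only Case C passes through all the rules without conflict or ambiguity.

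**Size of one error.** The one usable input is the planned sample of 30 children (Synopsis, 1.1).

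- Change in an ADE proportion per misclassified child = 1/N = 1/30 = 0.033, or 3.3 percentage points.

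The number of misclassified children cannot be estimated. The documents give neither the number expected to wash out nor a rate of worsening among them.

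**Can other provisions close the gap?**

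- The Schedule of Activities lists an adverse event assessment, marked at follow-up only. No rule for all-cause events stands behind it.
- Section 7.1.1 asks that adverse experiences present at withdrawal be reported, but it refers to Section 8.3, whose recording and reporting rules are written for ADEs.
- Section 8.3.4.3 mentions adverse events when assigning the judgment of expectedness. It adds no causality grade.
- The unanticipated-effect test in 8.3.2 uses the same three relatedness grades, as judged by the sponsor.
- The unanticipated-problem route in 8.4.1 requires, in general, that the event be unexpected and point to greater risk than was known. Ordinary worsening would not qualify.

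**The case against.** The strongest reply is that ADE was probably substituted for adverse event in standard text. The heading of 8.3 speaks of adverse events, several sections use that term, and the scope sentence in 8.3.5 makes sense only if all events were meant. That is a plausible account of how the conflict arose. It does not remove it, because no section supplies an all-cause recording rule or a grade for unrelated events.

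A reader might infer that every deterioration becomes at least a Possible device effect. The documents do not support this. Possible requires an inconclusive alternative explanation, so worsening clearly explained by stopping a stimulant does not meet it. Section 8.3.6 also asks for the rationale behind the causality assessment, so a non-device cause can be written down. What remains is that the event still carries the ADE label and no grade reflects the rationale.

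A reader might also infer that all washout-related worsening inflates the ADE count. That goes too far. Worsening that starts before Day 0 precedes the recording window and may be left out altogether. Criterion 6 in Section 5.1 limits washout to children judged inadequately managed on their medication, which bears on how many would worsen. Section 7.1.1 lists disease progression separately from adverse events, so how ADHD worsening is to be classed is itself open.

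Third, a reader might speak of a biased ADE rate. The plan specifies no such rate: there is no safety objective or endpoint in Section 3 and no safety analysis in Section 9. The point is confined to what any ADE tabulation would mean if one were produced. Over-attribution is also the cautious direction, and 8.3.4.2 says openly that the device is always to be suspected. That is a fair stance on doubtful cases, but it does not help where the cause is clear.

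Finally, the case report form and the Manual of Procedures are not in the documents. The form may already have a box for unrelated events.

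**Conclusion.** The concern holds as an internal conflict among Sections 8.3.1, 8.3.4.2 and 8.3.5. As written, a deterioration after enrollment with a clear non-device cause is labelled a device effect and fits no grade, and other unrelated events have no rule requiring them to be recorded. With one arm there is no concurrent comparison to expose the misattribution.

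The size is 3.3 percentage points per misclassified child. This assumes 30 children in the denominator; a smaller denominator makes the step larger. No total can be given, and no direction can be claimed for the overall count, since some events would be over-attributed and others left out.

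This should be corrected, but it does not threaten the study's main conclusion. It concerns how the safety record is kept in a small pilot whose primary endpoint is EEG-based.

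**What to change.** Five changes to the text:

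1. In 8.3.5, require all adverse events to be recorded as adverse events, including deterioration of a baseline condition, and remove the automatic ADE label.
2. In 8.3.4.2, add a Not related grade with a short definition.
3. In 8.3.1, define ADEs as the recorded adverse events rated Possible or higher, and bring 8.2 and 8.3.6 into line.
4. State that both all adverse events and ADEs will be reported.
5. In 8.3.5, reconcile the enrollment start of recording with the wider wording on deterioration, so that it is clear whether the washout period before Day 0 is covered.

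A listing that shows which children washed out of stimulants would help interpretation but is optional; with 30 children the subgroups would be small.

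The cost is one more category on the event form (none if the form already has it), a few sentences of protocol text, and slightly more events to record. The changes affect recording and reporting only, not how any child is treated.
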